Eustachian tube dysfunction is a poorly defined and understood clinical entity. While it is agreed upon that it is the primary etiology of chronic otitis media, particularly in adults, the exact physiology has been elusive. While many different theories have been proposed with evidence presented in addition, *Cummings* (Flint, *et al.*) describes two key physiological changes, whether it be mechanical obstruction (e.g., adenoid hypertrophy) or functional (normal anatomy with poor function). The former is likely more common in children with the latter best described in patients with cleft palate. Purely anatomical comparisons have not provided a definite etiology for why some individuals have significantly greater dysfunction.

In describing the clinical entity of Eustachian tube dysfunction, the literature varies between symptom descriptions, objective findings, and clinical outcomes (ie, need for surgery, etc.). Even when using objective findings, there is disagreement as to what degree of negative pressure on tympanometry constitutes Eustachian tube dysfunction. Attempts to measure function have been unsuccessful. A recent review by Norman, *et al.* found such significant variation in how ETD was defined in the literature that it was felt that no reasonable conclusions could be drawn regarding specific, consistent diagnostic criteria. While multiple symptom score indices have been proposed, including the Eustachian tube dysfunction questionnaire (ETDQ-7, Figure 1), they have not reached widespread use.

Figure 1. The Seven Item Eustachian Tube Dysfunction Questionnaire (ETDQ-7).

Over the past 1 month, how much has each of the following been a problem for you?	Severe Problem						
	No Problem	Moderate Problem					
1. Pressure in the ears?	1	2	3	4	5	6	7
2. Pain in the ears?	1	2	3	4	5	6	7
3. A feeling that your ears are clogged or “under water”?	1	2	3	4	5	6	7
4. Ear symptoms when you have a cold or sinusitis?	1	2	3	4	5	6	7
5. Crackling or popping sounds in the ears?	1	2	3	4	5	6	7
6. Ringing in the ears?	1	2	3	4	5	6	7
7. A feeling that your hearing is muffled?	1	2	3	4	5	6	7

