Treatment of ETD has also been elusive. While many methods have been proposed, including but not limited to devices such as the Otovent (Kestrel Medical, United Kingdom), surgical interventions such as balloon dilation, myringotomy with ventilation tube placement, laser coagulation, and others, none has provided sufficient data to prove a long-term benefit of the stated intervention. The value of preventing progression of chronic otitis media and its sequelae – including cholesteatoma, hearing loss, severe infections, and need for repeated surgical interventions – is unquestioned.

Continuous positive air pressure therapy

Continuous positive air pressure therapy (CPAP) is a highly successful treatment of an increasingly common problem – obstructive sleep apnea (OSA). Patients using CPAP for OSA have been evaluated in regard to middle ear function. Common otologic complaints related to CPAP include aural fullness and the development of serous otitis media. On the whole, CPAP use is quite safe for the middle ear, although rare case reports have suggested association with negative side effects including a single report of perilymph fistula formation. The most likely mechanism by which the ears are affected by CPAP is that air is forced into the Eustachian tube. Multiple studies have found higher middle ear pressures with CPAP use, although in patients without ETD, the middle ear pressure is likely to revert to a normal pressure. The impact of CPAP on the middle ear still has significant room for investigation.

Hypothesis to be Tested

There is a specific CPAP pressure at which individuals’ Eustachian tubes will allow air to be transmitted to middle ear. We will be able to correlate this to initial middle ear pressure.

Primary outcome measure: CPAP pressure required for middle ear insufflation.

Secondary outcome measures:

- Change in middle ear pressure with CPAP use
- Otoscopic findings
- Patient symptom survey (ETDQ-7)

Study Design: Biomedical

1. Will controls be used? No
2. What is the study design? Cohort study
3. Does the study involve a placebo? No

Human Participants

Ages: 18-99

Sex: M or F

Race: Any

Subjects- see below

1. **Provide target # of subjects (at all sites) needed to complete protocol.** 29
2. **Describe expected rate of screen failure/ dropouts/withdrawals from all sites.** 5%
3. **How many subjects will be enrolled at all sites?** 31
4. **How many subjects will sign a consent form under this UVa protocol?** 31

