5. **Provide an estimated time line for the study.**

After IRB approval, we anticipate completion of enrollment and study completion within 2 months. Data analysis will be concluded within 6 months of study initiation. No follow up is required.

Inclusion/Exclusion Criteria

1. List the criteria for inclusion

- Age \geq 18
- No use of CPAP within past 30 days
- Individuals presenting to the UVA otolaryngology clinic who are otherwise healthy

2. List the criteria for exclusion

- Pre-existing cardiopulmonary disease that presents a risk with CPAP use
- Inability to tolerate CPAP
- Recent otologic surgery

3. List any restrictions on use of other drugs or treatments. None

Statistical Considerations

1. Is stratification/randomization involved?

As there will be no comparison group, there will not be stratification or randomization. Any grouping will be performed in the data analysis portion based on data acquired within the study.

2. What are the statistical considerations for the protocol?

Primary endpoint:

- CPAP pressure at which a significant change in middle ear pressure occurs

Secondary endpoints:

- Tympanometry
- Otoscopy
- ETDQ-7

3. Provide a justification for the sample size used in this protocol.

We anticipate accruing 5-10 participants per week. The accrual goal will be 32, with an interim analysis at 16. We anticipate a very low dropout rate, but will account for a 5% rate. Based on calculations assuming a -0.500 correlation between “opening pressure” (CPAP pressure) and starting middle ear pressure, 29 participants are needed to show statistically significant differences. There is no required follow up, so this provides minimal drop-out risk.

4. What is your plan for primary variable analysis?

We will perform Spearman correlation calculations to estimate the relationship of CPAP pressure at which the ears “pop” to the initial and final tympanometric pressure as well as the change in tympanometric pressure.

5. What is your plan for secondary variable analysis?

We will use t-tests and/or ANOVA to assess the relationship of the above pressures to ETDQ-7 responses as well as using ROC curve analyses to determine if there is a true tympanometric pressure cut point to define ETD.

6. Have you been working with a statistician in designing this protocol? No

7. Will data from multiple sites be combined during analysis? No

Biomedical Research

1. What will be done in this protocol?

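### An ETD cut point picked from the ROC curve in about 29–32 participants will, on average, look more accurate than it is, and the plan has no interval, optimism correction or separate data.

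*Combined protocol and SAP*

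**What the plan says.** Statistical Considerations, item 5 (secondary variable analysis) plans t-tests and/or ANOVA relating the pressures to ETDQ-7 responses. In a separate clause it plans "using ROC curve analyses to determine if there is a true tympanometric pressure cut point to define ETD". It does not say how ETD status will be assigned for the ROC, how a cut would be selected, which accuracy measures would be reported, or how uncertainty would be shown.

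Item 1 of the same section, answering whether stratification or randomization is involved, adds: "Any grouping will be performed in the data analysis portion based on data acquired within the study". The Background explains the interest in a threshold: "there is disagreement as to what degree of negative pressure on tympanometry constitutes Eustachian tube dysfunction".

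The data come from one site, with no comparison group. The sample size was set for the primary correlation: "29 participants are needed to show statistically significant differences". The section on human participants says "How many subjects will be enrolled at all sites? 31", and the sample-size item says "The accrual goal will be 32, with an interim analysis at 16". No size or precision target is given for the ROC analysis.

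**The concern.** A threshold read off an ROC curve is the one that best separates these particular participants, chance differences included. Measuring its sensitivity and specificity in the same participants counts that chance fit as accuracy. The effect is small in large samples and substantial with about 30 people, of whom perhaps 6 to 16 have the condition.

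The Background calls the ETD threshold unsettled. A cut from this study, presented as a candidate for the true one with uncorrected accuracy, could add another definition to that literature that would not perform as well in new patients.

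**Working it through.** **1. The plan's own figure.** The text reads "Based on calculations assuming a -0.500 correlation between" opening pressure and starting middle ear pressure. Alpha and power are not stated; two-sided 0.05 and 80% are assumed because they reproduce the figure.

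n = ((1.960 + 0.842) / atanh(0.5))² + 3 = (2.802 / 0.5493)² + 3 = 29.01

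This agrees with 29. On dropout the plan says "We anticipate a very low dropout rate, but will account for a 5% rate"; 29 / 0.95 = 30.5, which rounds up to the 31 enrolled. The size is therefore explained entirely by the correlation.

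**2. Model for the ROC (all assumed).** Pressure is normal with SD 1, mean 0 without ETD and mean −d with ETD, where d = √2 · Φ⁻¹(AUC). For AUC 0.70, d = 1.414 × 0.524 = 0.74. A value below the cut c is called ETD. The cut maximises J = sensitivity + specificity − 1 in the sample. Its true performance in new patients is sensitivity Φ(c + d) and specificity 1 − Φ(c), so true J = Φ(c + d) − Φ(c). The documents give neither the ETD share nor the AUC, so ranges are used: 6, 9 or 14 cases of 29 (about 20%, 30% and 50%) and AUC 0.5 to 0.9.

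**3. Results, n = 29, 20,000 simulated studies per row.**

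| ETD cases | True AUC | Apparent J | True J | Overstatement | Studies overstated |
|---|---|---|---|---|---|
| 6 | 0.50 | 0.25 | 0.00 | 0.25 | 97% |
| 6 | 0.70 | 0.48 | 0.25 | 0.23 | 94% |
| 6 | 0.90 | 0.76 | 0.59 | 0.17 | 89% |
| 9 | 0.50 | 0.22 | 0.00 | 0.22 | 97% |
| 9 | 0.70 | 0.45 | 0.25 | 0.20 | 93% |
| 9 | 0.90 | 0.74 | 0.60 | 0.15 | 88% |
| 14 | 0.50 | 0.20 | 0.00 | 0.20 | 97% |
| 14 | 0.70 | 0.43 | 0.25 | 0.18 | 92% |
| 14 | 0.90 | 0.73 | 0.60 | 0.13 | 88% |

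With 9 cases and AUC 0.70, apparent sensitivity and specificity average 0.753 and 0.695 (J = 0.753 + 0.695 − 1 = 0.448). In new patients the same cuts give 0.617 and 0.634 (J = 0.251). Halving the overstatement in J gives about 7 to 12 percentage points on the average of sensitivity and specificity.

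**4. Other sizes.** At n = 32 the overstatement is again 0.13–0.25, in 86–97% of studies; a repeat simulation put the lowest share at 84%. If both ears were counted as 58 independent units (17 cases), which would be generous, it would be 0.10–0.16. At n = 200 (60 cases) it falls to 0.05–0.09.

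**5. What is and is not biased.** With 9 cases and AUC 0.70, the mean estimated AUC equals the true value, with SD 0.107. The 95% half-width is 1.96 × 0.107 = 0.21. The selected cut itself ranges over about 2.3 SD of pressure (2.5th to 97.5th percentile), so its location is poorly determined.

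**6. How far a bootstrap helps.** Repeating the cut selection in each resample and subtracting the estimated optimism brings J at AUC 0.70 down to about 0.31–0.35, against a true 0.25. That is roughly half to two thirds of the excess.

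**The case against.** Several points on the other side stand.

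- **The plan promises no particular accuracy figure.** If only the AUC is reported, with direction fixed by the hypothesis, nothing is inflated. The point is therefore conditional on a cut being chosen and its accuracy quoted. That is the ordinary product of an ROC search for a cut point, but it is not stated.
- **The wording asks whether a true cut exists.** It leaves room for the answer no, so the plan should not be read as asserting in advance that it will establish one.
- **Overstatement is an average tendency.** In some simulated studies the apparent figure was at or below the true one.
- **The analysis is secondary,** and the device appendix confirms that results will not be used in participants' care.

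A reader might also infer from item 1 that the ROC cut will define the t-test groups, or that groups will be tuned to the data, and so expect a false-positive rate far above 5%. The documents do not support this. Item 5 relates pressures to ETDQ-7 responses, and item 1 says only that groups come from study data, which a fixed ETDQ-7 threshold would satisfy. A search over all splits for the smallest p-value would inflate error badly, but no such search is described. Simulating reuse of a Youden cut under the null gave rejection rates of 4.5–5.1% when the tested variable was independent of the ETD label and about 7% when it correlated 0.5 with the label score. They reached 12–14% only when the test reused the very score that defined the label.

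Finally, there is a more basic gap: no ETD reference is named for the ROC. The protocol's opening rationale describes ETD by negative tympanometric pressure. If that were the reference, the ROC would be circular, and no correction could be run meaningfully until another is named.

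**Conclusion.** The concern holds in conditional form. If a cut is chosen from this curve and judged in the same 29 to 32 participants, its sensitivity and specificity will on average be overstated. J is too high by about 0.13–0.25, in roughly 84–97% of simulated studies, and a marker with no information would still show an apparent J of about 0.19–0.25. These sizes rest on an assumed ETD share of 20–50%, a normal marker and Youden selection. The direction was the same in every setting tried. The bias is relative to whatever ETD label is used: with an imperfect symptom score as reference, error against true ETD could go either way. The AUC is imprecise, not inflated, and the primary Spearman analysis is untouched. The plan should be changed, but this does not threaten the main result.

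**What to change.** Reword item 5 along these lines:

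> ROC analysis is exploratory. ETD status for the ROC is defined in advance by a reference that does not use tympanometry (for example a fixed ETDQ-7 threshold, already collected). The main result is the AUC with 95% CI. Any data-selected cut point is reported with a bootstrap 95% CI and optimism-corrected sensitivity and specificity, is described as needing confirmation in independent data, and is not used to form groups for other tests in this study.

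The stated aim should become exploring a candidate cut point, not determining whether there is a true one. The selection rule should be named, and the bootstrap must repeat the selection in every resample.

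The cost is protocol wording and a bootstrap run, with no added participants or procedures. Reported accuracy will be less favourable. Because the correction leaves a third to a half of the optimism at this size, the exploratory label and the interval are needed alongside it.

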In theory, patients with Eustachian tube dysfunction as defined by negative pressure on tympanometry will have more resistance in the Eustachian tube. Thus, the pressure required to open should be higher than the pressure in patients with normal function. This relationship has never been evaluated. It would have an impact not only when considering CPAP as a treatment modality, but also when considering CPAP in post-operative patients undergoing otologic surgery. We hypothesize an inverse relationship between middle ear pressure and air pressure as delivered by CPAP required to create both subjective (“popping” the ears) and objective (tympanometric and otoscopic) increase in middle ear pressure. We will begin recruiting participants from clinic and the general population. Each individual participant will be assigned a participant ID. The participant will be brought to the exam room and fitted with a new CPAP mask. Photodocumentation of otoscopic examination will be obtained for baseline as well as tympanometric measurement. Starting at a set pressure, the patient will be given a set number of breaths. Then, the setting will be increased until a maximum tolerable pressure is reached (no higher than 20 cm H₂O). The participant will be asked to notify the examiner when he or she has a sensation of his ears “popping”, and that level will be documented. Photodocumentation and tympanometric measurement will be obtained. These will be used to plot correlation between opening pressure and both initial middle ear pressure as observed on tympanometry and otoscopic evaluations. The Sade classification scheme will be used to grade otoscopic findings. These findings will be analyzed using SPSS and tests include Spearman correlations, t-tests, and Wilcoxon Rank-Sum Test.

Background

1. Provide the scientific background, rationale and relevance of this project.

Eustachian tube dysfunction and chronic otitis media

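### The planned ROC analysis cannot show that a true tympanometric cut point for ETD exists, because its usual outputs return a cut whether or not there is a threshold

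*Combined protocol and SAP*

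**What the plan says.** Statistical Considerations, item 5 (secondary variable analysis) relates the pressures to ETDQ-7 responses by t-tests or ANOVA, and adds "using ROC curve analyses to determine if there is a true tympanometric pressure cut point to define ETD". Nothing else in the document describes the ROC analysis. It gives no reference standard for ETD, no ETDQ-7 score cut-off, no hypothesis about the AUC, no rule for choosing a cut, no comparison of a threshold with a gradient, and no validation. The list of tests in the opening summary does not include ROC analysis.

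Three other places bear on the point:

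- The Background says that "there is disagreement as to what degree of negative pressure on tympanometry constitutes Eustachian tube dysfunction".
- The opening summary refers to "patients with Eustachian tube dysfunction as defined by negative pressure on tympanometry".
- Statistical Considerations, item 1 says that "Any grouping will be performed in the data analysis portion based on data acquired within the study".

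The only sample-size reasoning (item 3) concerns the primary correlation. It starts from "assuming a -0.500 correlation between “opening pressure” (CPAP pressure) and starting middle ear pressure" and concludes that "29 participants are needed to show statistically significant differences".

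**The concern.** Item 5 asks an existence question: is there a pressure at which ETD status truly changes? The competing explanation is that the risk of ETD rises gradually as pressure falls, so that any cut is a convention. The AUC answers a different question, namely how well pressure ranks people with and without ETD. A best cut is the maximum of a criterion over the observed pressures, and a maximum is available in almost any data set. Neither output sets a threshold against a gradient, and no other analysis in the plan does so.

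At stake is the secondary conclusion. The protocol itself presents the cut-off as disputed. If a small study reported a true cut point on the strength of an AUC or a best cut, it would add a number to that dispute that its analysis does not support. A larger sample or a validation set would not cure this while the conclusion rests on those two outputs.

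**Working it through.** **1. The plan's own figure.** Item 3 gives a correlation of -0.500 and 29 participants. Alpha and power are not stated; two-sided 0.05 and 80% are assumed because they reproduce the figure. By Fisher's z:

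n = ((1.960 + 0.842) / atanh(0.5))² + 3 = (2.802 / 0.5493)² + 3 = 29.01.

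With 5% dropout, 29 / 0.95 = 30.5, so 31, as the Human Participants section states; item 3 gives an accrual goal of 32. The 29 is therefore sound for the primary correlation under these assumptions. It relates opening pressure to starting middle ear pressure and says nothing about the ROC aim.

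**2. Assumptions for the ROC check.** None of these is in the documents.

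- Pressure is normally distributed, and n = 29 unless stated.
- For the AUC test: symptom score = -r × pressure + noise, ETD = score above the sample median, and the AUC is compared with 0.5 by the rank-sum test at two-sided 5%. The relation is smooth, with no threshold.
- For the best cut: ETD is binary, with (i) no relation, (ii) a logistic gradient of slope 1.5 per SD, or (iii) a true step in risk from 0.76 to 0.24 at the middle of the pressure range. The best cut maximises the Youden index (sensitivity + specificity - 1).

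**3. Best cut and AUC under three truths, n = 29.**

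| Truth | Best Youden index above 0 | Mean best Youden index | Mean AUC |
|---|---|---|---|
| No relation | about 96% | 0.21 | 0.50 |
| Smooth gradient | 100% | 0.59 | 0.81 |
| True step | 100% | 0.57 | 0.76 |

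A check by hand for the step: sensitivity and specificity at the step are both 0.76, so the true AUC is (0.76 + 0.76) / 2 = 0.76, which agrees with the simulation. The true Youden index is 0.76 + 0.76 - 1 = 0.52, and the maximum found in samples of 29 averages 0.57. Here the gradient, which has no threshold, scores slightly higher than the step on both measures.

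**4. AUC test when the truth is a smooth gradient.**

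| Assumed r | Significant, n = 29 | Significant, n = 32 |
|---|---|---|
| 0.3 | about 23% | about 25% |
| 0.5 | about 56% | about 61% |
| 0.7 | about 91% | about 93% |

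A different model (probit, ETD share 25% to 50%) gives 19-24%, 49-57% and 84-91% at n = 29. A true step with a 50-point jump in risk gives significance in about 65%, so a significant AUC does not point to a step.

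**5. Stability of the chosen cut.** With a smooth gradient at correlation 0.5 and an ETD share of 50%, the selected cut runs from -0.8 to +0.8 SD of pressure (5th to 95th percentile).

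**6. Could 29 to 32 participants settle the question by another method?** Choosing by AIC between a linear logistic model and the best single step, at n = 29, wrongly picks the step in 47-62% of smooth data sets and rightly picks it in 81-83% of step data sets. At n = 300 the wrong picks fall to 0-9% and the right picks reach 100%.

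**The case against.** The strongest reply is that the investigators may mean only a defensible diagnostic cut-off. ROC analysis is the usual tool for choosing one, and a useful cut-off needs no biological jump. This is a fair reading in light of the Background, and on it only the word *true* and the phrasing as an existence question are at fault. But item 5 does say that the analysis will decide whether such a point exists, so the wording needs repair on either reading.

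Three stronger readings are tempting and are not supported.

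- *The plan will usually, or whenever pressure and ETD are related at all, declare a true cut point.* The documents state no null, no AUC test and no rule. Under an AUC test the rate is only about 23% at r = 0.3 and 56% at r = 0.5. Near-certainty arises only under a rule of reporting any best cut, which the plan does not state. The -0.500 cannot be borrowed, because it belongs to a different pair of variables.
- *A ROC curve holds no information about a threshold.* That is true of the AUC and the best Youden index, but not of the whole curve. Its slope at each pressure is the likelihood ratio. The step above gives two straight segments with slopes 0.76 / 0.24 = 3.2 and 0.24 / 0.76 = 0.32, whereas the slope under the gradient falls smoothly. This shape is visible in a very large sample; the plan does not propose to examine it.
- *A direct test of a straight line against a line plus one step would settle the matter.* It rejects for smooth curvature as well. With no step present, it rejected in 13-56% of data sets at n = 29 across sigmoid, hinge and exponential shapes, and in 88-100% at n = 300. ETDQ-7 items are bounded at 1 and 7, so curvature is plausible, and the test would create the very claim to be avoided.

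It is also fair to say that the missing reference standard is the more basic gap. If ETD is defined by tympanometry, as in the opening summary, the ROC analysis becomes circular. Naming a reference standard is necessary but would not by itself make the existence conclusion follow.

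**Conclusion.** The point holds in a limited form. The usual outputs of the planned ROC analysis measure discrimination and will almost always supply a cut, so they cannot support a conclusion that a true cut point exists. At n = 29, a positive best Youden index appears in about 96% of trials with no association and 100% with a smooth gradient, and gradient and step are close on both AUC and Youden index.

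The sizes rest on assumed normal pressures, a median split or logistic risk, and assumed correlations; they illustrate and do not predict this study. The logical point does not depend on them.

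This is a minor matter of purpose and wording in a secondary analysis. It does not touch the primary Spearman analysis or participants' safety, and the protocol's device appendix says results will not be used in the subjects' care.

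**What to change.** In Statistical Considerations, item 5, replace the stated purpose of the ROC analysis with:

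> ROC analysis will estimate how well initial tympanometric pressure discriminates ETD, defined by an ETDQ-7 score cut-off fixed before analysis and not by tympanometry (AUC with 95% CI). Any best cut will be reported as exploratory, with a bootstrap interval, and will not be taken as evidence that a true cut point exists.

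Add a plot of ETDQ-7 score against initial pressure with a smooth curve, so that readers can see the shape of the relation. Do not add a line-versus-step test.

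The cost is a change of wording, a score cut-off chosen and recorded in advance, one plot and one bootstrap on data already planned. No participants or procedures are added. The downside is that the secondary claim becomes more modest.

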- Each individual participant will be assigned a participant ID.
- The participant will be brought to the exam room and fitted with a new CPAP mask.
- Photo-documentation of otoscopic examination will be obtained for baseline as well as tympanometric measurement.
- Starting at a set pressure, the patient will be given a set number of breaths. Then, the setting will be increased until the maximum tolerable pressure or a maximum pressure of 20 cm H₂O has been reached.
- The patient will be asked to notify the examiner when he or she has a sensation of his ears “popping”, and that level will be documented.
- Photo-documentation and tympanometric measurement will be obtained.

2. List the procedures, in bullet form, that will be done for RESEARCH PURPOSES as stipulated in this protocol.

- Tympanometry
- Otoscopy
- Short term use of CPAP (10 minutes)
- ETDQ-7 for our research purposes.

3. Will you be using data/specimens in this study that were collected previously, with the use of a research consent form, from another research study? No

4. Will any of the procedures listed in item # 2 have the potential to identify an incidental finding? This includes ALL procedures, assessments and evaluations that are being done for RESEARCH PURPOSES that may or may not be considered investigational. yes

This examination(s) utilizes non-standard/investigational, technique, equipment, etc. It is impossible to determine the significance of such results, therefore abnormalities will not be shared with the subject because the meaning of the exam is not yet proven and is of unknown clinical benefit.

5. Do any of the procedures listed above, under question # 2, utilize any imaging procedures for RESEARCH PURPOSES? No

6. Will you be using viable embryos? No

7. Will you be using embryonic stem cells? No

8. Are any aspects of the study kept secret from the participants? No

9. Is any deception used in the study? No

10. If this protocol involves study treatment, explain how a subject will be transitioned from study treatment when they have completed their participation in the study. NA

11. Will your study involve measures (C-SSRS/BID/SCID etc.) used to assess for depression and/or suicidality for research purposes? No

Taping/Photography

1. Will participants be recorded on audiotape? No

2. Will participants be photographed or recorded on videotape? Yes

▶ IF YES, answer the following questions.

2a. Will their faces be shown? No

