2b. What steps will be taken to protect the privacy of the subjects?

The device used to take the photographs (iPhone) will be secured per UVA protocol and only used for research purposes. The images will only be tied to a participant ID. The images will only be of the ear drum and as such will not allow for identification if seen.

2c. What data will be captured from the photo or videotape that could not be obtained in other ways? Image of the tympanic membrane (ear drum). This cannot otherwise be reviewed in a blinded fashion.

2d. How is this data critical to this research?

This provides an additional clinical measurement that allows for analysis of patients.

2e. When will data from the tapes be transcribed?

Within one month of obtaining them they will be transferred to a secure file and deleted from the portable device.

2f. When will the tapes be destroyed?At the conclusion of the study.

2g. Will participants be photographed, recorded or videotaped without their knowledge?
No

3. If a subject withdraws from the study how will you withdraw them from the audiotape, videotape or photograph? Delete the files.

Data and Safety Monitoring Plan

1. Definition:

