2.5 What are the criteria for breaking the blind/mask?

Other: If an otoscopic finding were identified that was not noted on clinical exam.

2.6 How will subject withdrawals/dropouts be reported to the IRB prior to study completion?

IRB-HSR continuation status form

3. Adverse Event / Unanticipated Problem Recording and Reporting

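### The no-disclosure rule for incidental findings covers otoscopy, but its stated reason does not fit a clinically recognisable ear drum abnormality

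*Combined protocol and SAP*

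**What the plan says.** Biomedical Research, item 2, lists four research procedures: tympanometry, otoscopy, short-term CPAP and the ETDQ-7. Item 4 asks whether any of them could reveal an incidental finding. The scope of the question is wide: "This includes ALL procedures, assessments and evaluations that are being done for RESEARCH PURPOSES that may or may not be considered investigational". The answer is yes. A single paragraph then describes the examinations as investigational, says the significance of their results cannot be determined, and concludes that "abnormalities will not be shared with the subject because the meaning of the exam is not yet proven". No procedure is excepted.

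Other sections treat otoscopy differently:

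- The opening summary, before Background: "The Sade classification scheme will be used to grade otoscopic findings".
- Taping/Photography, item 2d, on the ear drum image: "This provides an additional clinical measurement that allows for analysis of patients". Item 2c gives the reason for photographing: "This cannot otherwise be reviewed in a blinded fashion".
- Data and Safety Monitoring Plan 2.5 gives one criterion for breaking the blind: "If an otoscopic finding were identified that was not noted on clinical exam".
- Taping/Photography, item 2f, says when the images are destroyed: "At the conclusion of the study".

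**The concern.** One reason is applied to procedures of different standing. The response of the ear to CPAP pressure is the research question, so its meaning is unknown by design. An ear drum abnormality that an otolaryngologist would recognise does not become uninterpretable because it was seen during a study.

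What is at stake is a finding that the clinical examination missed and the research photograph shows. Background names cholesteatoma among the sequelae of chronic otitis media and regards the value of preventing progression as beyond question. Under item 4 as written, the study would not tell the subject about such a finding. There is no later visit at which it might come up, and the image is not kept after the study ends.

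**Working it through.** No arithmetic applies. The documents give no rate of ear drum findings missed at clinical examination, and the point depends on no alpha, power or effect size. The check is whether item 4's reason holds for each procedure that could yield an abnormality, and whether another section supplies the missing step.

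**1. Does the rule reach otoscopy?** Yes. Otoscopy is listed in item 2, item 4 refers to everything listed there, and no exception is written.

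**2. Does the reason fit each procedure?**

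- *CPAP opening pressure: it fits.* The Unapproved Device Use appendix names only the CPAP machine as used outside its approval, and reports 0 previous human uses of this kind.
- *Tympanometry: it fits in part.* Background says "there is disagreement as to what degree of negative pressure on tympanometry constitutes Eustachian tube dysfunction", and Statistical Considerations, item 5, plans ROC analyses to look for a cut point. The interpretation of a pressure as evidence of dysfunction is therefore unsettled. Nowhere is tympanometry itself called a non-standard technique, so the support covers that interpretation and not every tympanometric result.
- *Otoscopy: it does not fit a recognisable abnormality.* The protocol grades the findings with a named scheme, calls the image a clinical measurement, and uses the clinical examination as the comparator in 2.5. Photographing with an iPhone (Taping/Photography, item 2b) may limit image quality. That is a reason to confirm a finding, not a reason to call its meaning unknown.

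**3. Does 2.5 supply the missing step?** Only in part. It foresees the situation in question and allows the blind to be broken. It does not say who is informed, it requires no follow-up, and it does not lift the rule in item 4.

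**4. Is there another route to the subject?**

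- *Adverse event reporting:* no. Under Data and Safety Monitoring Plan 1.1 a pre-existing condition counts only if it worsens. Under 3.1 only events that are both related and serious are recorded. A pre-existing ear drum lesion would ordinarily meet neither condition.
- *Follow-up:* none is planned (Human Participants, item 5).
- *Treating clinicians:* a partial route. The Privacy Plan gives them access to the data, and Appendix: Recruitment, item 2c, says that team members who approach subjects are their health care providers. Access allows a clinician to learn of the finding but does not oblige anyone to pass it on.

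**5. How many people does the rule cover?** All who enrol: 31 in Human Participants, with an accrual goal of 32 in Statistical Considerations, item 3. How many would have a finding of this kind cannot be estimated from the documents.

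**The case against.** The best defence is that 2.5 is itself the otoscopy exception. Item 4 is general text and 2.5 is specific. Images carry only a participant ID, so breaking the blind makes sense mainly as a way to link the image to a patient so that someone can act. Item 4 also ties its rule to investigational techniques, so one can argue it was never aimed at standard otoscopy. Part of this stands: the protocol clearly regards such a finding as worth acting on. But 2.5 stops at unblinding, and a coordinator following item 4 literally would find no permission to tell the subject.

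A second argument is that the risk is small, and that stands. The inclusion criteria admit people attending the otolaryngology clinic, 2.5 presupposes a clinical examination, and treating clinicians may see the data. Harm needs a significant finding that was missed clinically, showed on the photograph, and was then not acted on. The opening summary also mentions recruiting from the general population, who might have had no clinical examination. The inclusion criteria do not list that source, so little weight should rest on it.

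Third, the Unapproved Device Use appendix confirms that results will stay out of clinical care. That confirmation is given for the CPAP machine. It could be argued that photographs taken after CPAP are results of its use. Requiring the treating clinician to confirm the abnormality in ordinary care largely meets this, because the subject is then told what the clinician has confirmed.

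A reader might infer that the protocol intends serious ear disease to be concealed, or that it forbids a treating clinician from re-examining the ear and discussing what is seen. The documents support neither. Item 4 governs how research findings are shared and places no limit on ordinary care, and 2.5 points towards action. Nor do they support the view that all tympanometric results are of unknown meaning.

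**Conclusion.** The point holds as a wording gap that bears on participant safety. The non-disclosure rule is blanket, its reason does not cover a clinically recognisable ear drum abnormality, and 2.5 anticipates such a finding without saying who is told. The residual risk is small and unquantified, and no analysis, sample size or error rate is affected. It is worth changing because the change is cheap, at the lowest level of priority.

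Two assumptions carry the conclusion. The first is that item 4 is read literally, as the operative instruction to study staff. The second is that the consent form does not already deal with the matter. That text is not available, so it should not be inferred that subjects are told nothing about incidental findings. If the consent form does provide for disclosure, what remains is to bring item 4 into line with it.

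**What to change.** In Biomedical Research, item 4, limit non-disclosure to the CPAP opening pressure and to the interpretation of tympanometric pressure as evidence of Eustachian tube dysfunction. Then add:

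> A clinically recognisable ear drum abnormality seen on otoscopy or on the research photograph, and not already recorded at the clinical examination, will be reviewed by the PI and reported to the treating clinician, who will inform the subject once it is confirmed.

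In Data and Safety Monitoring Plan 2.5, add:

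> When the blind is broken for this reason, the PI informs the treating clinician, who informs the subject and decides on follow-up.

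The wording should commit the clinician to informing the subject; permission to do so would leave the gap open. The limit on tympanometry should stay with the disputed interpretation and not become a bar on all tympanometric results.

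The cost is one IRB modification and an occasional repeat look at the ear in ordinary care. Some flags from iPhone images will not be confirmed, which is why confirmation comes before disclosure. The investigational readings remain undisclosed, and the planned analyses are untouched.
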